# 15. PROPOSED SAMPLE SIZE

#### Primary Hypothesis

To demonstrate the superiority of biomarker-led IS withdrawal over maintenance IS for hard clinical outcomes such as long term survival or incidence of IS-related side effects, the trial would require an unrealistically large sample size and a very lengthy follow-up. Notwithstanding, given the well known potential long-term benefits of IS withdrawal and the health-economic implications, the current study has been designed and powered to test the hypothesis that the IS weaning under the novel "Biomarker-based" strategy (Arm B+) is superior to Weaning All (Arm A), with respect to the proportion of participants who, having started the IS withdrawal protocol, complete it successfully without undergoing allograft rejection. Comparing arms A and B+ will show the utility of the biomarker as a clinical decision tool, as a function of its predictive accuracy. We have established that for the biomarker to drive safe IS withdrawal its Positive Predictive Value (*PPV* =  $\frac{Number Actually Tolerant}{Number Biomarker+}$ ) should be no less than 0.80, which would result into a statistically significant difference in the proportion of successfully weaned participants between arms A and B+. If the biomaker's PPV was 0.50, then participants in arm B+ would be no

better than taken at random, and there would be no difference with respect to arm A. Additionally, for the biomarker test to be considered successfully validated for clinical use, its sensitivity as estimated within arm A should be at least 0.70.

Expectations:

- **Biomarker Allocation:** Approximately 50% of participants will be positive for the biomarker (17).
- Arm A: 50% Successfully weaned participants vs.
- Arm B+: Under H0: 50% successfully weaned participants (if PPV = 0.50); under H1: 80% or more successfully weaned participants (if PPV ≥ 0.80).

100 participants would be sufficient to show superiority of Arm B+ compared to Arm A, with 90% power and 5% type I error rate, assuming an allocation ratio of 2:1 between arms A and B+ (given 50% biomarker positive). The resulting sample size including participants allocated to arm B- would be 134 subjects. To account for dropouts, the final sample size will be increased in 10%, resulting in a total of 148 participants.

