# 16. STATISTICAL ANALYSIS

#### 16.1 Primary Analysis

To test for superiority of arm B+, compared to arm A, we will compare the proportion of successfully weaned participants in each arm using generalized linear mixed models (GLMM) (logistic regression) with random effects for study centre, as a factor used in the minimisation procedure. Potential confounding will be examined, as part of sensitivity analysis, for the following covariates: (study centre, age at randomization, time from transplantation at randomization, a binary indicator of whether the participant was receiving a second drug at baseline). The primary outcome will be analysed per Intention-to-Treat, i.e. participants allocated to arms A or B+ who do not start the weaning protocol or initiate weaning but do not complete it, will be treated as 'failures'. To ultimately validate the clinical utility of the biomarker, 2 further conditions will need to be met: 1) the confidence interval of the proportion of successes in arm B+ should include 0.80 and exclude 0.50; and 2) the confidence interval of the test's sensitivity as estimated in arm A should include 0.70 and exclude 0.50.

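### The three-part validation rule in section 16.1 is not covered by the sample size: at the protocol's own minimum values it is met in only about 48-61% of trials

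*Protocol*

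**What the plan says.** Section 15 bases the sample size on one comparison: "100 participants would be sufficient to show superiority of Arm B+ compared to Arm A, with 90% power and 5% type I error rate". The calculation takes two Arm A participants for every one in B+, because half are expected to be biomarker-positive. The rates are 50% success in Arm A against 80% or more in Arm B+ if the PPV is at least 0.80. Adding Arm B- gives 134, and 10% for dropout gives 148.

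The same section adds a requirement with no sample size attached: "for the biomarker test to be considered successfully validated for clinical use, its sensitivity as estimated within arm A should be at least 0.70".

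Section 16.1 turns this into a decision rule. Besides superiority, two conditions must hold before clinical utility is regarded as validated. The interval for the B+ success proportion must include 0.80 and exclude 0.50. For sensitivity, "the confidence interval of the test's sensitivity as estimated in arm A should include 0.70 and exclude 0.50". Neither section gives the probability of meeting all three together.

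**The concern.** Validating the biomarker is the stated purpose of the trial (synopsis), and accurate identification of tolerant recipients is part of the primary objective (section 5.2). The decision on validation therefore matters as much as the superiority test, but only that test was used to set N.

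Two features of the sensitivity condition make it the weak link.

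- **Few participants inform it.** It uses only Arm A participants who turn out to be tolerant, about half of that arm. The biomarker is measured in everyone before randomisation (section 8.1), and B+ participants follow the same weaning protocol as Arm A (section 8.3), but none of the Arm B information is used.
- **It has an upper trap.** The interval must contain 0.70, so a test good enough to push its whole interval above 0.70 fails. The 0.80 clause for B+ works the same way.

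The risk is that a biomarker meeting the sponsor's own criteria is declared not validated.

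**Working it through.** **1. Reproduce the stated N.** Inputs from section 15: 0.50 vs 0.80, A:B+ = 2:1, 5% type I error (taken as two-sided), 90% power. With the unpooled two-proportion formula:

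n_A = (1.960 + 1.282)² × (0.25 + 0.16/0.5) / 0.30² = 10.51 × 0.57 / 0.09 = 66.5; n_B+ = 33.3; total 99.8, i.e. 100. About 33-34 more in B- gives 134, and 134 × 1.10 = 147.4, i.e. 148. The stated 90% therefore reproduces, for superiority alone.

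**2. What the inputs imply for sensitivity.** Sensitivity = (share positive × PPV) / success rate.

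- Planning inputs: 0.50 × 0.80 / 0.50 = 0.80.
- Minimum values: sensitivity 0.70 with PPV 0.80 and 50% success needs a positive share of 0.70 × 0.50 / 0.80 = 43.75%.

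**3. The sensitivity condition alone.** Tolerant participants expected in Arm A: 67 × 0.5 = 33.5, or 74 × 0.5 = 37. Section 16.1 gives no interval level; 95% is assumed, as in section 16.3. At true sensitivity 0.70, the chance that the interval excludes 0.50 is 59.9% with n=33 and 69.8% with n=37. Letting the number of tolerant participants vary, it is 60-68% at N=134 and 66-73% at N=148 (exact to Wilson interval).

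**4. The upper trap.** Take 32 of 37 tolerant participants biomarker-positive (0.865). The Wilson centre is (0.865 + 3.84/74)/(1 + 3.84/37) = 0.831 and the half-width 0.110, so the lower limit is about 0.72. The interval lies above 0.70, and condition 2 fails because the test did too well.

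**5. All three conditions together.** Simulation with allocation balanced on the biomarker, a likelihood-ratio test for superiority, exact and Wilson 95% intervals, and no dropout, centre effects or interim stopping:

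| True values | Rule | N=134 | N=148 |
|---|---|---|---|
| PPV 0.80, sensitivity 0.70 | as written | 48-56% | 56-61% |
| PPV 0.80, sensitivity 0.70 | intervals exclude 0.50 only | 50-58% | 57-64% |

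For PPV 0.80 and sensitivity 0.80, the rule as written is met in 66-70% across the two sample sizes; with intervals excluding 0.50 only, in 82-89%.

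At the minimum values superiority alone holds in 0.84 (N=134) and 0.87 (N=148), so most of the loss comes from the sensitivity condition. At sensitivity 0.80 most of it comes from the include clauses. Other choices of superiority test, interval (including Wald) and B+ share widen the as-written range at the minimum values to 43-56% at N=134 and 51-61% at N=148.

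**6. Using everyone's data.** Let P be the positive share in both arms, PPV the success rate in A+ and B+ together, and F the success rate in A-. Then sensitivity = P × PPV / [P × PPV + (1-P) × F]. Check at the minimum values: F = 0.50 × 0.30 / 0.5625 = 0.267, so sensitivity = 0.35 / (0.35 + 0.15) = 0.70.

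With a logit delta-method interval, the sensitivity condition at 0.70 rises to about 80% (N=134) and 84% (N=148). The joint rule with intervals excluding 0.50 rises to about 68% and 74%. Coverage is about 95.5%, and false exclusion at true sensitivity 0.50 is 2.0%.

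If the requirement to include 0.70 is kept, however, the narrower interval lowers the joint pass rate at sensitivity 0.80 and N=148 from 0.67-0.70 to 0.64.

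**The case against.** **The 90% is correctly labelled.** A reader might infer that the protocol promises 90% power for validation. It does not: section 15 names the B+ versus A comparison and states the sensitivity requirement separately. This objection stands. The gap is a missing figure for the full rule, not a false one.

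**Sensitivity 0.70 is not the planning value.** It is stated as a minimum, and the planning inputs imply 0.80. That also stands, so 48-61% describes the least favourable acceptable case. It is still a realistic one: the recalibrated assay in section 4.1.1 had a sensitivity of 72%, and section 16.3 uses 70% as its own target. Nor does moving to 0.80 rescue the rule as written, which then passes in only 66-70%.

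**Section 16.3 gives 80% power for sensitivity.** That is for an interim look at 37 Arm A participants, of whom about 18-19 would be tolerant. It does not address the final joint decision.

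**Arm A is the natural place to estimate sensitivity.** It is the only arm in which biomarker-positive and biomarker-negative participants are both weaned, so the estimate needs no combination across arms. This is fair: the choice is valid, but imprecise. Pooling assumes equal success in A+ and B+. Minimisation on the biomarker, a common weaning protocol, and blinding of participants undergoing withdrawal and their physicians to the result all support that.

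**This could be left to the SAP.** An interval method could. The decision rule, the restriction to Arm A and the power statement are fixed in the protocol itself.

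**Conclusion.** The point holds in this form: the sample size covers superiority, while the validation decision in section 16.1 also needs a sensitivity condition that is imprecisely estimated and include clauses that can fail a better test. The rule as written is met in about 48-56% (N=134) or 56-61% (N=148) of trials at the minimum values, and in about 66-70% at the planning inputs.

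The documents do not support reading this as a fault in the superiority calculation, which reproduces, or as a claim that the trial has about 50-60% power whatever the biomarker's quality. If the intervals need only exclude 0.50, power at the planning inputs is 82-89%.

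The figures assume 95% exact or Wilson intervals and no dropout, centre effects or interim stopping. The N=148 values are on the favourable side, since the extra participants were added to absorb dropout and non-completers count as failures.

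**What to change.** Make three changes together.

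1. **Section 16.1, condition 2.** Estimate sensitivity from all randomised participants with the formula in step 6, using a logit delta-method or bootstrap interval. Keep the Arm A-only estimate as a sensitivity analysis.
2. **Section 16.1, both conditions.** Replace the include clauses so that an interval lying wholly above the target does not fail: lower limit above 0.50, and upper limit not below 0.70 for sensitivity or 0.80 for the B+ proportion. Without this, change 1 lowers the pass rate of a better test.
3. **Section 15.** Report the power of the full three-condition rule at sensitivity 0.70 and at 0.80, naming the interval method and the dropout assumption.

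The cost is protocol wording and a few lines of code, with no added patients or procedures. There are two downsides: the pooled estimate relies on equal success in A+ and B+, and the disclosed power will look less favourable than 90%. The changes are not a complete cure, since at sensitivity 0.70 joint power with intervals excluding 0.50 is still only about 68% (N=134) or 74% (N=148). That is why the third change is needed as well.

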# 16.2 Secondary Analysis

For the exploratory analysis of secondary outcomes, we will use GLMM to adjust stated outcome(s) for study site as a random effect. Multivariate models will include, as fixed effects, the main effects of treatment strategy arm and biomarker status, as well as the interaction term. Secondary analyses are considered exploratory and will not be adjusted for multiple comparisons. A survival analysis approach will additionally be adopted to examine times to acute rejection in patients assigned to IS weaning. For the analysis of serial measures we will use mixed effects regression with random

effects for study subject, as well as for study centre. The stability of the biomarker signature at the final study visist will be tested with GLMM: logistic regression for a binary classification signature and linear regression for a continuous diagnostic score before classification cut-off. The model will include, as fixed effects, the baseline classification or, correspondingly, the baseline estimated probability of tolerance, the main effect of treatment strategy arm and their interaction, as well as study centre, as a random effect. The effect of co-variates (same as for the analysis of the primary outcome and additionally baseline drugs and duration of weaning) will be examined as part of sensitivity analysis. The effect of potential mechanistic mediators on primary and secondary outcomes will be evaluated using generalized latent mixed models (31). This will allow us to consider different models of causation (32). Missing baseline data required for covariate adjustment should not represent an issue for the primary analysis. Patters of missingness of post-randomisation assessments will be examined in relation to the co-variates used for adjustment. If there are two or more outcome time points, missing post-randomisation assessments will be dealt with by fitting GLMMs to all the available data using maximum likelihood methods. If post-treatment variables are found to be predictive of drop-out, multiple imputation will be considered. (R statistics software will be used for statistical analyses (http://www.R-project.org).

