#### 9.2 Secondary endpoints

#### 9.2.1 The secondary clinical endpoints of the trial are defined as:

- Rejection (incidence, severity, timing, steroid resistant rejection, chronic rejection).
- Reasons for failure of IS withdrawal.
- Requirement for IS re-institution despite successful IS withdrawal on the basis of the histological criteria described in Table 5.
- Progression of graft fibrosis in tolerant participants and those on maintenance IS.
- Graft loss.
- All–cause mortality.
- Proportion of tolerant participants remaining free of rejection at 3 years post IS withdrawal.
- Renal function at 1, 2 and 3 years after enrollment.
- Change in co-morbidities associated with IS use (hypertension, cardiovascular risk profile, diabetes mellitus, hyperlipidemia, malignancy).
- Stability of the biomarker signature between baseline and last study visit.
- HrQOL changes associated with IS withdrawal.
- Pharmacoeconomic impact of IS withdrawal.
- Fibroscan:

1- To assess if drug withdrawal results in sequential changes in liver stiffness over time in patients considered tolerant.

2- To evaluate if development of an episode of rejection in patients who do not successfully discontinue immunosuppression increases liver stiffness measurements.

3- To compare changes in liver stiffness over time in patients who remain on maintenance immunosuppression and those who undergo drug weaning.

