#### 10.11 Transient elastography assessment (FibroScan®)

All participants will undergo transient elastography assessments using FibroScan at screening and every 12 months (visits M12, M24, M36, M48). Elastography results in isolation should not be employed to modify the management of study participants (e.g. modifying immunosuppressive doses or indicating a for-cause biopsy).

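### Section 16.2 states the terms of the secondary models without each continuous outcome's own baseline value, which costs precision to the extent that baseline is not used in some other way

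*Protocol*

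**What the plan says.** Section 16.2 sets out the general secondary model. Site is a random effect ("we will use GLMM to adjust stated outcome(s) for study site as a random effect"), and "Multivariate models will include, as fixed effects, the main effects of treatment strategy arm and biomarker status, as well as the interaction term". Repeated outcomes have their own sentence, which begins "For the analysis of serial measures we will use mixed effects regression with random" and goes on to name effects for subject and for centre. It does not say whether the baseline measurement is a response, a covariate or unused.

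The sensitivity covariates are described as "same as for the analysis of the primary outcome and additionally baseline drugs and duration of weaning". The primary list referred to, in section 16.1, is "study centre, age at randomization, time from transplantation at randomization, a binary indicator of whether the participant was receiving a second drug at baseline". The outcome's own baseline value appears in neither.

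One secondary model does carry a baseline term. The signature-stability model includes "the baseline classification or, correspondingly, the baseline estimated probability of tolerance".

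Section 9.2.1 defines one of the affected endpoints as a level: "Renal function at 1, 2 and 3 years after enrollment". Co-morbidities, quality of life and liver stiffness are worded there as changes.

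The baselines exist. The renal measures are taken at the baseline visit (section 10.3.1). The metabolic panel and questionnaires are taken at M0 (section 10.3.3, Randomisation Visit, and Table 2). For liver stiffness, section 10.11 states "All participants will undergo transient elastography assessments using FibroScan at screening and every 12 months".

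**The concern.** A continuous outcome measured before and after randomisation in the same patient is usually estimated more precisely when its own baseline is in the model. Section 16.2 names the model terms, names a baseline term for one outcome, and leaves it out for the others, so the gap lies in a stated model.

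It matters most for one contrast. Both arms wean biomarker-positive participants, so withdrawal against maintenance is randomised only among the biomarker-negative: those in Arm A, who wean, against Arm B-, who do not. These are small groups, and minimisation (section 8.2.2) balances only site and biomarker result. The objectives on co-morbidities and quality of life, and the FibroScan comparison of maintenance with weaning, lean on this contrast.

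**Working it through.** **Group sizes.** The plan states no standard deviation, correlation, power or precision for any secondary outcome, so there is no secondary figure to reproduce. The sample size in section 15, from which the group sizes follow, does reproduce. For 50% v 80%, 2:1, two-sided 5%, 90% power and unpooled variance:

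- n(B+) = (1.960 + 1.282)² × (0.16 + 0.25/2) / 0.30² = 33.3, and 3 × 33.3 = 99.8, against the stated 100.
- 67 + 67 = 134, and 134 × 1.10 = 147.4, against the stated 148.

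With half of each arm biomarker-negative, A- v B- has 148/4 = 37 per group, or 134/4 = 33.5 after the planned dropout.

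**Single follow-up visit.** Let ρ be the baseline to follow-up correlation, which is assumed throughout. Relative to a model that ignores baseline (variance 1), a change score has variance 2(1 − ρ) and baseline as a covariate has 1 − ρ². The precision lost against the covariate model is ρ² if baseline is ignored and (1 − ρ)/2 if change is analysed.

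| ρ | 1 − ρ² | 1/(1 − ρ²) | Lost, baseline ignored | Lost, change score |
|---|---|---|---|---|
| 0.5 | 0.75 | 1.33 | 25% | 25% |
| 0.6 | 0.64 | 1.56 | 36% | 20% |
| 0.7 | 0.51 | 1.96 | 49% | 15% |
| 0.8 | 0.36 | 2.78 | 64% | 10% |

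At ρ = 0.3 the loss from ignoring baseline is only 9%.

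**Detectable difference for A- v B-.** With 80% power and two-sided 5% (conventions chosen for illustration), the difference in SD units is (1.960 + 0.842) × √(2/n × (1 − ρ²)).

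| n per group | Baseline ignored | ρ = 0.5 | ρ = 0.6 | ρ = 0.7 | ρ = 0.8 |
|---|---|---|---|---|---|
| 37 | 0.65 | 0.56 | 0.52 | 0.47 | 0.39 |
| 33 | 0.69 | 0.60 | 0.55 | 0.49 | 0.41 |

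**Chance imbalance.** The standard error of the baseline difference is √(2/37) = 0.23 SD. In a follow-up-only model a share ρ of any such difference is expected to carry over, for example 0.7 × 0.23 = 0.16 SD. This is part of the variance above and is not a bias.

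**Serial model.** Four follow-ups (as for FibroScan), ρ = 0.7 between all visits, 134 participants, 40 simulated trials. Variance of the average arm effect relative to follow-up only:

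- baseline as a covariate: 0.38
- baseline as a response, equal arm means at baseline: 0.38
- baseline as a response, arms free at baseline: 0.50, a loss of 1 − 0.38/0.50 = 24%

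The closed form agrees. Follow-up only has variance (1 + 3 × 0.7)/4 = 0.775, covariate 0.775 − 0.49 = 0.285, and arms free 0.775 + 1 − 1.4 = 0.375. The loss is 1 − 0.285/0.375 = 24%.

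For a four-visit average, the loss with baseline ignored is 4ρ²/(1 + 3ρ): 40%, 51%, 63% and 75% at ρ = 0.5 to 0.8. With arms free at baseline it is (1 − ρ)²/((1 + 3ρ)/4 + 1 − 2ρ): 40%, 32%, 24% and 16%.

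**The case against.** The strongest reply has four parts.

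- **The list may not be complete.** Section 16.2 says what the models will include and does not say that nothing else enters. A statistical analysis plan, not seen here, may add baseline terms. This stands as a caution, but the section does name covariates, including one baseline term, so adding the missing one improves a stated model.
- **The serial sentence governs most of these outcomes.** Table 2 repeats them through M48. If baseline is a response with equal arm means, nothing is lost. This stands as a possibility. The text never says that baseline is a response, and with arms left free at baseline a loss remains.
- **Most of the endpoints are worded as changes.** A change score already uses baseline, and the loss at one visit is then 10% to 25% over the range assumed. That is right. Renal function is the exception, and section 16.2 does not say that change scores are modelled.
- **The analyses are exploratory.** No decision rule depends on them. This limits the consequence.

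Two stronger readings are tempting. A reader might infer that the plan discards a third to two thirds of the available precision for all these outcomes. That needs ρ between about 0.58 (√(1/3)) and 0.82 (√(2/3)) and a baseline that is wholly unused. The protocol supplies no correlation, and the serial and change wording leave the second condition open. A reader might also infer that baseline imbalance biases the comparison of arms. It does not: allocation is randomised, and the omission only widens the interval.

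**Conclusion.** The omission is real and worth correcting, and its size is conditional. If baseline is otherwise unused, most clearly for renal function as a level, the variance at one visit is 1.3 to 2.8 times larger for assumed ρ of 0.5 to 0.8. If change scores are used or baseline is a response, the loss at one visit is about 0 to 25% over the same range. Contrasts averaged over four visits can lose more, as shown in the working. The A- v B- contrast suffers most: at 37 per group its detectable difference is 0.65 SD without baseline and 0.56 to 0.39 SD with it. All of this rests on assumed correlations, equal variance at each visit and, for the serial results, equal correlation between visits. The matter is one of precision in exploratory analyses and does not affect the primary comparison.

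**What to change.** Add one sentence to section 16.2, in either form:

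- every model of a continuous secondary outcome, for single visits and serial measures alike, includes the outcome's own baseline value as a fixed effect; or
- the baseline value enters the serial model as a response, with arm means constrained to be equal at baseline.

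Name the baseline for each outcome: screening for liver stiffness, M0 for the metabolic panel and questionnaires, and one stated visit for renal function. Define it identically in all arms. A definition tied to the start of weaning would not work, because Arm B- never weans.

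One point needs a note. Section 10.3.3 places the Randomisation Visit after the email with the randomisation result, so M0 questionnaires may be completed when allocation is known. Both forms of the fix assume a baseline unaffected by allocation. For the self-reported scores, record whether the questionnaire preceded disclosure and add a sensitivity analysis without the baseline term.

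The cost is a sentence and that note. No new assessments are needed.

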#### 4.2 **Risks and benefits**

**Benefits:** Chronic IS is associated with a variety of life threatening side effects following liver transplantation, including infection, malignancy, hypertension, diabetes, nephrotoxicity and cardiovascular diseases. Calcineurin inhibitor induced nephrotoxicity, in particular, is responsible for a significant rate of chronic renal failure, need for renal replacement therapy and increased mortality (18-20). Elimination of calcineurin inhibitors may preserve waning renal function and avoid the associated morbidity and mortality risk. Identification of a reproducible and reliable tolerance signature will allow tailoring of IS to individual patient characteristics. It may also identify critical pathways responsible for the tolerant state that can be therapeutically exploited to induce tolerance in those who do not achieve it spontaneously.

**Risks:** While there is abundant information in the literature suggesting that in carefully selected liver recipients IS withdrawal is feasible and safe, the procedure is not without risk, as it can induce immunologically-mediated allograft rejection. In this regard, the main risks of IS withdrawal are: 1) acute and/or chronic rejection; 2) silent development of allograft fibrosis; 3) potential complications associated with the need to increase IS to treat rejection episodes; and 4) graft loss or patient mortality as a consequence of risks 1-3.

*Rejection-associated graft injury or graft loss:* A fundamental premise of the current trial is that rejection that develops under the close surveillance of a controlled trial will be easily reversed and will not result in permanent allograft damage. This is based on the results of the recent multi-centre clinical trials described above, in which rejection episodes occurring during IS withdrawal were generally mild to moderate in histological severity and easily treated, and no graft losses were observed (12-14). While theoretically possible, severe rejection leading to graft loss, retransplantation or patient death is extremely unlikely, and has only been reported in two cases (3, 5). It should be emphasized that these 2 patients were not enrolled in clinical trials with close surveillance protocols. As such, criteria for patient selection and the process for IS withdrawal were

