### 5.3 Secondary Objectives:

- 1) To establish the safety of biomarker-guided IS withdrawal.
- 2) To determine the health-economic impact of withdrawing IS in liver transplant recipients and to assess how much this cost is influenced by the use of a diagnostic test of operational tolerance.
- 3) To assess the effect of IS withdrawal on the quality of life of liver transplant recipients.
- 4) To determine the extent to which IS withdrawal improve drug-related co-morbidities.
- 5) To investigate if liver transplant recipients under IS become operationally tolerant over time.
- 6) To determine if the presence of donor-specific anti-HLA antibodies influence the success of IS withdrawal, and whether IS withdrawal promotes the development of anti-HLA antibodies in liver transplant recipients.
- 7) To explore the association between operational liver transplant tolerance, iron metabolism, immunosenescence, and specific gut microbiome profiles.

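### The interaction GLMM set for the secondary outcomes is likely to be non-estimable for graft loss and for severe, steroid-resistant or chronic rejection

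*Protocol*

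**What the plan says.** Section 16.2 opens: "For the exploratory analysis of secondary outcomes, we will use GLMM to adjust stated outcome(s) for study site as a random effect". It then fixes the terms: "Multivariate models will include, as fixed effects, the main effects of treatment strategy arm and biomarker status, as well as the interaction term". It also says: "Secondary analyses are considered exploratory and will not be adjusted for multiple comparisons". The only other analysis it gives for a rejection endpoint is a survival analysis of time to acute rejection in participants assigned to weaning. It does not name the link for these outcomes (logistic is implied for binary ones), and it names no test.

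Section 9.2.1 puts "Rejection (incidence, severity, timing, steroid resistant rejection, chronic rejection", graft loss and "All–cause mortality" among the secondary clinical endpoints. The first secondary objective in section 5.3 is "To establish the safety of biomarker-guided IS withdrawal".

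On expected frequency, section 4.2 reports that in earlier multi-centre trials "rejection episodes occurring during IS withdrawal were generally mild to moderate in histological severity and easily treated, and no graft losses were observed", and that "severe rejection leading to graft loss, retransplantation or patient death is extremely unlikely, and has only been reported in two cases". It expects rejection that needs strong regimens to be just as rare. No percentage is given for any of these outcomes, and nothing is said about the expected rate of all-cause death. The 5% in section 14 is a trigger for review of the severe-rejection composite, not an expected rate.

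**The concern.** Arm, biomarker status and their interaction use one parameter for each of the four combinations of arm and biomarker. With a binary outcome, the fit simply reproduces the four observed proportions on the logit scale. A proportion of zero has a logit of minus infinity, so one empty cell (quasi-complete separation) leaves the coefficients that touch it without a finite estimate. Software then returns an arbitrary large coefficient with a very large standard error.

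The outcomes most exposed are those described as rarest, and they bear on the first secondary objective. B- stays on maintenance immunosuppression, so if weaning drives these events it is the likeliest cell to be empty. A- v B- is also the randomised comparison that shows what the test spares biomarker-negative recipients. At stake is whether the final report can give an effect estimate and interval for that comparison.

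**Working it through.** **Inputs.** 148 participants are randomised 1:1, minimised on site and biomarker result (section 8.2.2), and about 50% are biomarker-positive (section 15). Event rates are assumptions, because the protocol gives none.

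**Planned size.** Two-sided 5%, 90% power, 0.50 v 0.80, 2:1, unpooled variance: n in Arm A = (1.960 + 1.282)² × (0.25 + 0.16/0.5) / 0.30² ≈ 66.5, so 67 + 33 = 100. Adding B- gives 134, and 134 × 1.10 = 147.4, so 148. The plan's 100, 134 and 148 are reproduced. Each cell then holds 148/4 = 37.

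**Chance that the model cannot be estimated.** With rate p in every cell, P(a given cell is empty) = (1 − p)^37.

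- Any of four cells empty: 1 − [1 − (1 − p)^37]^4
- A- or B- empty: 1 − [1 − (1 − p)^37]^2

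| p | One cell empty | Any of four empty | A- or B- empty |
|---|---|---|---|
| 1% | 0.689 | 0.991 | 0.90 |
| 2% | 0.474 | 0.923 | 0.72 |
| 3% | 0.324 | 0.791 | 0.54 |
| 5% | 0.150 | 0.478 | 0.28 |

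If only 134 contribute (33.5 per cell), any-cell failure is 99%, 94%, 83% and 55%. With unequal rates (A- 5%, A+ and B+ 2%, B- 1%) it is 93%. At 10% in every cell it falls to 8%.

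**All-cause death.** Assuming 1%, 2% or 3% a year, four-year risk is 1 − (1 − r)^4 = 3.9%, 7.8% or 11.5%, and an empty cell occurs in 64%, 19% or 4% of trials. The problem there depends on a rate that the protocol does not state.

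**Illustration.** Events out of 37: A+ 1, A- 6, B+ 1, B- 0. The logistic fit, without the site effect and with biomarker-negative as reference, gives:

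- arm coefficient −21.9, SE about 13,000, Wald p = 0.999;
- likelihood-ratio test for arm plus interaction (2 df), p = 0.012; for A- v B- alone (1 df), p = 0.003;
- Firth estimate for the same arm coefficient, −2.74 (SE 1.51), which is finite;
- Fisher's exact test, A- v B- (6/37 v 0/37), p = 0.025; whole Arm A v whole Arm B (7/74 v 1/74), p = 0.063.

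The random site effect does not rescue the fit. With 8 events in A- instead of 6, and participants allocated to 14 sites at random, the mixed model gave an arm coefficient of −19.8 with SE about 5,770, p = 0.997 and convergence warnings.

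Which coefficient fails depends on which cell is empty. With events of 0, 8, 0 and 1 in A+, A-, B+ and B-, the arm coefficient stays finite (−2.30, p = 0.035), while those for biomarker status and the interaction do not.

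**Precision available.** For 0 events among the 74 + 37 = 111 weaned participants, the exact two-sided upper 95% limit is 1 − 0.025^(1/111) = 3.3%.

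**The case against.** A reader might infer that the planned model would report p near 1 for a real safety difference and so hide harm. The documents do not support that. Section 16.2 names no test, and the p of 0.999 belongs only to the Wald test of a coefficient touching the empty cell. The likelihood-ratio test on the same data and model gives 0.012.

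Nor does participant safety rest on this model. Under section 14 any death or graft loss pauses the study for DMEC review, and the severe-rejection composite is monitored with an exact one-tailed 90% interval.

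It is also fair to say that scarce events, more than the model, limit what can be learnt. At true rates of 5% in A- and 1% in B-, Fisher's test of A- v B- has power of about 0.7%. Section 15 already concedes that hard clinical outcomes are out of reach at this size.

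Finally, section 16.2 does not forbid counts or exact intervals, the analyses are exploratory, and a fallback for sparse data may stand in the SAP, which is not shown.

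All of this stands, and it narrows the point. It does not remove it. The protocol writes down one model for these outcomes, and at low rates that model usually yields no usable estimate or Wald interval. A likelihood-ratio p-value does not supply the missing point estimate. Monitoring by the DMEC does not supply a final between-arm comparison.

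**Conclusion.** The point holds in limited form. For graft loss and for severe, steroid-resistant or chronic rejection, the interaction GLMM is likely to be non-estimable: an empty cell in 92% to 99% of trials if the rate is 1% to 2%, and in about half at 5%. For the A- v B- contrast alone, the figures are 72% to 90% and 28%. They rest on 37 per cell, a common rate in all cells and rates assumed from a qualitative statement. All-cause mortality belongs here only if a cell turns out empty. This is a reporting and estimation weakness in an exploratory analysis, not evidence that harm would go unseen.

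**What to change.** Add an exception to section 16.2 for graft loss and for severe, steroid-resistant or chronic rejection, and for all-cause mortality only if a cell has no events:

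- Report counts with exact (Clopper-Pearson) 95% confidence intervals for weaned (A+, A-, B+) and maintained (B-) participants.
- Compare Arm A with the whole of Arm B, and A- with B-, by an exact method or by Firth-penalised logistic regression on arm and biomarker status without the interaction. A likelihood-ratio test is also acceptable.
- State the attainable precision, for example that 0/111 weaned gives an upper 95% limit of 3.3%.
- Keep the interaction GLMM for outcomes with events in every cell.

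The cost is a few lines of text, with no extra data or participants. The downside is that these few outcomes lose the adjustment for centre. Power stays low whichever method is used.
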